23.2 INSTITUTIONAL REVIEW BOARD (IRB) APPROVAL AND CONSENT

It is expected that the IRB will have the proper representation and function in accordance with federally mandated regulations. The IRB must approve the consent form and protocol.

In obtaining and documenting informed consent, the Investigator should comply with the applicable regulatory requirement(s) and should adhere to Good Clinical Practice (GCP) and to ethical principles that have their origin in the Declaration of Helsinki.

Before recruitment and enrollment onto this study, the patient will be given a full explanation of the study and will be given the opportunity to review the consent form. Each consent form must include all the relevant elements currently required by the FDA Regulations and local or state regulations. Once this essential information has been provided to the patient and the Investigator is assured that the patient understands the implications of participating in the study, the patient will be asked to give consent to participate in the study by signing an IRB-approved consent form.

Prior to a patient's participation in the trial, the written informed consent form should be signed and personally dated by the patient and by the person who conducted the informed consent discussion. A copy of the signed consent form should be provided to the patient.

24. DATA MANAGEMENT AND MONITORING/AUDITING

24.1 DATA MONITORING COMMITTEE/DATA SAFETY MONITORING BOARD (DMC/DSMB)

This trial will be monitored by the MPN-RC Data Safety Monitoring Board according to the established Charter.

An External Data and Safety Monitoring Board has been established. All members have experience and expertise in clinical trials. DSMB members are not directly involved in any phase of MPN-RC clinical

in Patients with Accelerated/Blast-phase Myeloproliferative Neoplasm or Chronicphase Myelofibrosis with an IDH2 Mutation

(Myeloproliferative Neoplasms Research Consortium [MPN-RC] 119)

trials and they have no major financial or intellectual conflict of interest that would prevent them from objectively reviewing the interim data and providing advice to the Trials Steering Committees and the Clinical Advisory Group. They function independently of all other individuals, processes, and progress to ensure study integrity, monitor patient safety (providing quarterly safety reports), evaluate the results of interim analysis to assess efficacy, and make recommendations about protocol amendments and early termination to the Trials Steering Committees. The External Data Safety and Monitoring Board must meet at least two times a year.

24.2 MEDICAL MONITORING

MPN

It is the responsibility of the local institutional Principal Investigator to oversee the safety of the study at his/her site. This safety monitoring will include careful assessment and appropriate reporting of adverse events as noted above, as well as the construction and implementation of a site data and safetymonitoring plan. Medical monitoring will include a regular assessment of the number and type of serious adverse events.

24.3 MONITORING PLAN AND PERIOD OF OBSERVATION

The MPN-RC will monitor study progress on an on-going basis; this will include electronic and telephone correspondence between the central coordinating office and with individual investigators and/or their designees at other sites.

The Sponsor or the Sponsor designees, "study monitors," will monitor the study according to a predetermined monitoring plan (centrally and with on-site visits). The monitoring visit will provide the Sponsor with opportunity to:

- Evaluate the progress of the study
- Verify the accuracy and completeness of CRFs
- Assure that all protocol requirements, applicable laws and/or regulations, and Investigator's obligations are being fulfilled
- Resolve any inconsistencies in the study records

25. REGULATORY REQUIREMENTS

See the Regulatory Requirements section for a listing of required regulatory documents. All protocol amendments will be generated through and distributed by the MPN-RC Central Coordinating Office, which will also maintain records of IRB approval, amendments, SAEs, and annual reviews.

25.1 ADHERENCE TO THE PROTOCOL

Except for an emergency situation in which proper care for the protection, safety, and well-being of the study subject requires alternative treatment, the study shall be conducted exactly as described in the approved protocol.

25.2 EMERGENCY MODIFICATIONS

Investigators may implement a deviation from, or a change of, the protocol to eliminate an immediate hazard(s) to trial subjects without prior IRB approval.

25.3 OTHER REPORTABLE NEW INFORMATION AND PROTOCOL DEVIATIONS/VIOLATIONS

Confidential

in Patients with Accelerated/Blast-phase Myeloproliferative Neoplasm or Chronicphase Myelofibrosis with an IDH2 Mutation

(Myeloproliferative Neoplasms Research Consortium [MPN-RC] 119)

In accordance with BRANY IRB requirements, the following information must be reported within five (5) business days:

- Non-compliance with federal regulations governing human research or with the requirements or determinations of the IRB, or an allegation of such non-compliance.
- Failure to follow the protocol due to the action or inaction of the Investigator or research staff.
- Breach of confidentiality

MPN-RC

• Premature suspension or termination of the research by the Sponsor or Investigator.

25.4 AMENDMENTS TO THE PROTOCOL

Should amendments to the protocol be required, the amendments will be originated and documented by the Principal Investigator. It should also be noted that when an amendment to the protocol substantially alters the study design or the potential risk to the patient, a revised consent form might be required.

The written amendment, and if required the amended consent form, must be sent to the IRB for approval prior to implementation.

25.5 RECORD RETENTION

Study documentation includes all Case Report Forms, data correction forms or queries, source documents, Sponsor-Investigator correspondence, monitoring logs/letters, and regulatory documents (e.g., protocol and amendments, IRB correspondence and approval, signed patient consent forms).

Source documents include all recordings of observations or notations of clinical activities and all reports and records necessary for the evaluation and reconstruction of the clinical research study.

Government agency regulations and directives require that the Study Investigator must retain all study documentation pertaining to the conduct of a clinical trial. In the case of a study with a drug seeking regulatory approval and marketing, these documents shall be retained for at least two years after the last approval of marketing application in an International Conference on Harmonization (ICH) region. In all other cases, study documents should be kept on file until three years after the completion and final study report of this investigational study.

26. OBLIGATIONS OF INVESTIGATORS

The Principal Investigator is responsible for the conduct of the clinical trial at the site in accordance with Title 21 of the Code of Federal Regulations and/or the Declaration of Helsinki. The Principal Investigator is responsible for personally overseeing the treatment of all study patients. The Principal Investigator must assure that all study site personnel, including Sub-Investigators and other study staff members, adhere to the study protocol and all FDA/GCP/NCI regulations and guidelines regarding clinical trials both during and after study completion.

The Principal Investigator at each institution or site will be responsible for assuring that all the required data will be collected and entered onto the Case Report Forms. Periodically, monitoring visits will be conducted and the Principal Investigator will provide access to his/her original records to permit verification of proper entry of data. At the completion of the study, all case report forms will be reviewed by the Principal Investigator and will require his/her final signature to verify the accuracy of the data.

26.1 GOOD CLINICAL PRACTICE

in Patients with Accelerated/Blast-phase Myeloproliferative Neoplasm or Chronicphase Myelofibrosis with an IDH2 Mutation

(Myeloproliferative Neoplasms Research Consortium [MPN-RC] 119)

The study will be conducted in accordance with the International Conference on Harmonization (ICH) for Good Clinical Practice (GCP) and the appropriate regulatory requirement(s). The Investigator should be thoroughly familiar with the appropriate use of the study drug as described in the protocol and Investigator's Brochure. Essential clinical documents should be maintained to demonstrate the validity of the study and the integrity of the data collected. Master files should be established at the beginning of the study, maintained for the duration of the study and retained according to the appropriate regulations.

26.2 ETHICAL CONSIDERATIONS

This study is to be conducted according to US and international standards of Good Clinical Practice (FDA Title 21 part 312 and International Conference on Harmonization guidelines), applicable government regulations and Institutional research policies and procedures.

This protocol and any amendments should be submitted to a properly constituted independent EC or IRB, in agreement with local legal prescriptions, for formal approval of the study conduct. The decision of the EC/IRB concerning the conduct of the study should be made in writing to the Investigator and a copy of this decision should be provided to the MPN-RC Central Office before commencement of this study. The Investigator should provide a list of EC/IRB members and their affiliate to the MPN-RC Central Office.

All subjects for this study will be provided a consent form describing this study and providing sufficient information for subjects to make an informed decision about their participation in this study. This consent form should be submitted with the protocol for review and approval by the EC/IRB for the study. The consent of a subject, using the EC/IRB-approved consent form, must be obtained before a subject is allowed to participate. This consent form must be signed by the subject or legally acceptable surrogate, and the Investigator obtaining the consent.

26.3 PATIENT INFORMATION AND INFORMED CONSENT

After the study has been fully explained, written informed consent should be obtained from either the patient or his/her guardian or legal representative prior to study participation. The method of obtaining and documenting the informed consent and the contents of the consent should comply with ICH-GCP and all applicable regulatory requirement(s).

26.4 PATIENT CONFIDENTIALITY

Information about study subjects should be kept confidential and managed according to the requirements of the Health Insurance Portability and Accountability Act of 1996 (HIPAA). Those regulations require a signed subject authorization informing the subject of the following:

- What protected health information (PHI) will be collected from subjects in this study
- Who will have access to that information and why
- Who will use or disclose that information

The patient has the right to revoke their authorization for use of their PHI. In the event that a subject revokes authorization to collect or use PHI, the Investigator, by regulation, retains the ability to use all information collected prior to the revocation of subject authorization. For subjects that have revoked authorization to collect or use PHI, attempts should be made to obtain permission to collect at least vital status (i.e. that the subject is alive) at the end of their scheduled study period.

26.5 PROTOCOL COMPLIANCE

in Patients with Accelerated/Blast-phase Myeloproliferative Neoplasm or Chronicphase Myelofibrosis with an IDH2 Mutation

(Myeloproliferative Neoplasms Research Consortium [MPN-RC] 119)

The Investigator should conduct the study in compliance with the protocol given approval/favorable opinion by the IRB and the appropriate regulatory authority(ies). Changes to the protocol will require approval of the MPN-RC and written IRB approval/favorable opinion prior to implementation, except when the modification is needed to eliminate an immediate hazard(s) to patients. The MPN-RC will submit all protocol modifications to the regulatory authority(ies) in accordance with the governing regulations. Any departures from the protocol must be fully documented in the source documents.

26.6 MANAGEMENT OF INFORMATION

MPN-RC

The MPN-RC at Mount Sinai will maintain sponsorship authority at the Icahn School of Medicine at Mount Sinai School and all other participating sites.

Eligibility criteria will be confirmed using the electronic CRF. All inclusion and exclusion criteria are listed; the Investigator is obliged to fill in all items. Subjects are enrolled in the study only if he/she fulfills all inclusion and no exclusion criteria.

IRB approval for each site will be submitted to the MPN-RC Central Coordinating Office via e-mail (PDF file preferred) or fax:

MPN-RC Central Coordinating Office

Clinical Trials Manager MPN-RC Central Office [contact] [contact] Email: [contact] Office hours: Monday through Friday 9AM to 5PM EST/EDT

Upon receipt of these documents and confirmation of certification of the Study Investigators, the site will be granted access to the online registration system and case report forms.

In addition, all protocol amendments will be generated through and distributed by the MPN-RC Central Coordinating Office, which will also maintain records of IRB approval, amendments, SAEs, and annual reviews.

Serious adverse event reporting is detailed in the Reporting Requirement section of this protocol.

Protocol deviations will be reported to the MPN-RC Data Monitor and CTM:

CTM: [name] [contact] Email: [contact] Office hours: Monday through Friday 9AM to 5PM (EST)

Data Monitor: [name] [contact] Email: [contact] Office hours: Monday through Friday 8:00AM to 5:00 PM (CT)

The MPN-RC Principal Investigators will be notified as soon as possible (and within 7 days) of reporting and will be responsible for granting approval.

The MPN-RC will monitor study progress on an on-going basis; this will include electronic and telephone correspondence between the central coordinating office and with individual investigators at other sites.

26.7 DRUG ACCOUNTABILITY

in Patients with Accelerated/Blast-phase Myeloproliferative Neoplasm or Chronicphase Myelofibrosis with an IDH2 Mutation

(Myeloproliferative Neoplasms Research Consortium [MPN-RC] 119)

Accountability for the study drug at all study sites is the responsibility of the site Principal Investigator. The responsible Investigator at each participating center will ensure that the study drug is used only in accordance with this protocol, drug accountability records indicating the drug's delivery date to the site, inventory at the site, use by each patient, and return. Accountability records will include dates, quantities, lot numbers, expiration dates (if applicable), and patient numbers. Conditions of the excursion will be evaluated on a case by case basis and a memo indicating continued use or discontinuation of the drug product involved will be communicated.

26.8 SOURCE DOCUMENTS

Source data includes all information, original records of clinical findings, observations, or other activities in a clinical trial necessary for the reconstruction and evaluation of the trial. Source data are contained in source documents. Examples of these original documents, and data records include: hospital records, clinical and office charts, laboratory notes, memoranda, subjects' diaries or evaluation checklists, pharmacy dispensing records, recorded data from automated instruments, copies or transcriptions certified after verification as being accurate and complete, microfiches, photographic negatives, microfilm or magnetic media, x-rays, subject files, and records kept at the pharmacy, at the laboratories, and at medico-technical departments involved in the clinical trial.

26.9 CASE REPORT FORMS (CRF)

The study CRF is the primary data collection instrument for the study. All data requested on the CRF must be recorded. The CRFs may be found online at the MPN-RC website at (https://redcap2.mayo.edu/redcap/). The CRF Form Submission schedule is listed below:

MPN-RC #119 Form#	MPN-RC #119 FORM NAME	CRF SUBMISSION SCHEDULE
00	Recruitment Form	At Registration
01	Baseline	After Registration
02	Bone Marrow Report	At required time points specified in Table 5.
03	Cytogenetic	At required time points specified in Table 5.
04	Symptom Assessment Package	At required time points specified in Table 4.
05	Drug Dosage form	At required time points specified in Table 4.
06	Adverse Event form	At occurrence of Adverse Event
07	Cycle 1-2 Day 1 CRF	At Cycle 1-2 Day 1
08	Cycle 1-2 Day 8 CRF	At Cycle 1-2 Day 8
09	Cycle 1-2 Day 15 CRF	At Cycle 1-2 Day 15
10	Cycle 1-2 Day 22 CRF	At Cycle 1-2 Day 22
11	Cycle 3+ everyDay 1 CRF	At Cycle 3+ Day 1

Table 7. CRF Form Submission Schedule

in Patients with Accelerated/Blast-phase Myeloproliferative Neoplasm or Chronicphase Myelofibrosis with an IDH2 Mutation

	~ -	-					D	~		
- 1		velo	nrolifers	ntive	Neon	lacme	Research	Consortium	IMPN_RC	119)
	TAT.		promere		ιιυμ	103113	I (c)(a) (h)	Consol dum		11/)

MPN-RC #119 Form#	MPN-RC #119 FORM NAME	CRF SUBMISSION SCHEDULE
12	Off Treatment	At time of treatment withdrawal
13	Off Study	At time of off study, 30 days post treatment withdrawal

26.10 PREMATURE CLOSURE OF THE STUDY

This study may be prematurely terminated, if in the opinion of the MPN-RC Trial Steering Committee there is sufficient reasonable cause. Written notification documenting the reason for study termination will be provided to the Investigator by the terminating party.

Circumstances that may warrant termination include, but are not limited to:

- Determination of unexpected, significant, or unacceptable risk to patients
- Failure to enter patients at an acceptable rate
- Insufficient adherence to protocol requirements
- Insufficient complete and/or evaluable data
- Plans to modify, suspend or discontinue the development of the study drug

26.11 RECORD RETENTION

It is the Investigator's responsibility to retain study essential documents for at least 2 years after the last approval of a marketing application in their country and until there are no pending or contemplated marketing applications in their country or at least 2 years have elapsed since the formal discontinuation of clinical development of the investigational product. These documents must be retained at least 2 years following completion of the last follow-up on patients on active study. These documents should be retained for a longer period if required by an agreement with the Sponsor. In such an instance, it is the responsibility of the Sponsor to inform the Investigator/institution as to when these documents no longer need to be retained.

26.12 DATA MANAGEMENT

Study data will be recorded and managed using the Research Electronic Data Capture (REDCap) system developed by Vanderbilt University. Research Electronic Data Capture is a secure, web-based application designed to support data capture for research studies, providing:1) an intuitive interface for validated data entry; 2) audit trails for tracking data manipulation and export procedures; 3) automated export procedures for seamless data downloads to common statistical packages; and 4) procedures for importing data from external sources.

After IRB approval and site training, REDCap database access will be given to approved and trained individuals at each site. Each user will have a unique username/password assigned by the REDCap administrator at Mayo Clinic (where the MPN-RC Statistical and Data Center Core is located).

26.13 QUALITY ASSURANCE

Weekly registration reports will be generated to monitor patient accruals and completeness of registration data. Routine data quality reports will be generated to assess missing data and inconsistencies. Accrual rates and extent and accuracy of evaluations and follow-up will be monitored periodically throughout the study period and potential problems will be brought to the attention of the

in Patients with Accelerated/Blast-phase Myeloproliferative Neoplasm or Chronicphase Myelofibrosis with an IDH2 Mutation

(Myeloproliferative Neoplasms Research Consortium [MPN-RC] 119)

study team for discussion and action. Monthly teleconferences including the Principal Investigators and/or their designees from all sites will be held to expedite the reviews of toxicity and efficacy data.

27. WITHDRAWAL OF SUBJECTS

Treatment with study drugs is to be discontinued when any of the following occurs:

- Lack of any response by 6 cycles of combined enasidenib and ruxolitinib therapy (any effort should be made to provide therapy to the patient in a safe way for at least 3-6 cycles for proper assessment of potential efficacy).
- Adverse event(s) that, in the judgment of the Investigator, may cause severe or permanent harm or which rule out continuation of study drug
- Withdrawal of consent
- Lost to follow up
- Toxicity requiring dose modification/treatment suspension, without recovery to baseline, in a patient with less than a CRi
- Death

MPN-RC

The patient will have an end of study visit at 30 days after discontinuation of the protocol treatment ± 7 days to assess for AEs.

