3. STUDY SCHEMA

Eligible patients with signed consent who have completed all requisite screening tests and procedures are to start Cycle 1 Day 1 within 30 days of signing consent.

All adverse events captured during the first 28 days of treatment with Ruxolitinib and Enasidenib will be used to assess safety and tolerability in the first 6 patients on study.

Cycles will be a minimum of 28 days.

Following cycle 6, response will be assessed by IWG/ELN consensus criteria and patients will continue treatment if response was deemed a CR/CRi/PR or CBR for MPN-AP and MPN-BP patients. For chronic phase MF, response will include CR/PR and clinical improvement.

Patients will continue to be followed post treatment for long term survival every 3 months for up to 12 months by telephone encounter or medical record review to determine the following variables: alive versus deceased and type of current therapy.

*Ruxolitinib dosing based on platelet counts; Enasidenib 100 mg for MPN-AP or MPN-BP and 50 mg for chronic phase MF for cycle 1

in Patients with Accelerated/Blast-phase Myeloproliferative Neoplasm or Chronicphase Myelofibrosis with an IDH2 Mutation

(Myeloproliferative Neoplasms Research Consortium [MPN-RC] 119)

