As of 15 Apr 2016 in Study AG221-C-001, the overall response rate (ORR) (defined as complete response [CR] + CR with incomplete neutrophil recovery [CRi] + morphologic CR with incomplete platelet recovery [CRp] + partial response [PR] + marrow CR [mCR] + morphologic leukemia free state [MLFS]) among the 113 subjects in the dose escalation phase was 45.1% with a median time to first response of 1.9 months and a median time to best response of 3.7 months. Twenty-four of the 113 subjects (21.2%) achieved a best response of CR, with a median time to CR of 3.8 months. Responses occurred in all dosing groups (30 mg BID to 650 mg QD). Of the 176 subjects with R/R AML in the combined Phase 1 part of the study, the ORR was 40.3%, with a median duration of response of 5.8 months. Thirty-four of the 176 subjects (19.3%) achieved a CR, with a median duration of CR of 8.8 months. The ORR, CR, and median duration of response were similar in the subset of subjects who received the 100 mg daily dose compared with the total R/R AML population. Of the 71 responders among subjects with R/R AML, the median time to first response was 1.9 months and the median time to best response was 3.7 months. The median times to first response and best response were similar in the subset of subjects who received the 100 mg daily dose. At the time of data cutoff, median eventfree survival for subjects with R/R AML was 6.4 months (95% CI = 5.4, 7.5) and median overall survival was 9.3 months (95% CI = 8.2, 10.9).

This study⁴³ led to the Food and Drug Administration approval to enasidenib for the treatment of adult patients with relapsed or refractory acute myeloid leukemia with IDH2 mutation in August 2017.

Please refer to the current version of the enasidenib IB for detailed information concerning the available pharmacology, toxicology, drug metabolism, clinical studies, and AE profiles of enasidenib.

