If drug-related Grade 3 clinically relevant non-hematologic toxicity is attributable to one or both of the drugs (based on known adverse events profile), dose interruption of that particular drug(s) is mandatory. Patients who experience Grade 3 drug related clinically relevant non-hematological toxicity may be given a subsequent course one dose level below the previous course, but the patient must have recovered to Grade ≤ 1 before initiation of the next course. If attributable to ruxolitinib, dosing modifications in Tables 2a and 2b should be utilized. If attributable to enasidenib, dosing modification in Table 3b should be utilized. If a patient has drug-related clinically relevant Grade 4 non-hematologic toxicity, he/she will be taken off study. The dose of therapeutic agents can be decreased, at the discretion of treating physician, for chronic Grade 2 non-hematologic toxicity. Additionally, ruxolitinib dosage may be adjusted if patients develop decline in Creatinine clearance (CrCl) as calculated by the Cockcroft- Gault equation as follows: Reduce ruxolitinib dose by one dose level for patients with moderate (CrCl 30-59 mL/min) or severe renal impairment (CrCl 15-29 mL/min) if the patient is receiving a ruxolitinib dose of 10 mg BID or higher. (Per FDA package insert for ruxolitinib).

Myelosuppression and cytopenias are expected outcomes of MF disease processes and MF treatments and per se will not constitute adverse events except as follows: hematologic toxicity will be considered Grade 4 neutropenia with fever that does not clinically resolve within 14 days in the setting of optimal interventions or Grade 4 thrombocytopenia with clinically-significant bleeding. Dose interruption of the drug to which the adverse event is attributable is required. Patients may be given a subsequent course one dose level below the previous course, but the patient must have recovered to grade \leq baseline at study entry. The dose of therapeutic agents can be decreased, at the discretion of treating physician, for chronic Grade 3 hematologic toxicity.

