-4	5 QD	Stop treatment		
-5	Stop treatment			

* For patients with accelerated and blast phase MF, treatment will continue at the same dose regardless of platelet count.

Table 2b. Ruxolitinib Dose Adjustment for patients with chronic phase MF for thrombocytopenia or nonhematological AEs

Dos	e level	DOSE ADJUSTMENT FOR THROMBOCYTOPENIA		
		Plt>100 X10 ⁹ /L	Plt 50-100 X10 ⁹ /L	Plt 20-50 X10 ⁹ /L
	+1	20 BID	15 BID	N/A
DOSE ADJUSTMENT FOR NON- HEMATOLOGICAL AES	15 BID	10 BID	5 BID*	
	-1	10 BID	5 BID	5 QD
	-2	5 BID	5 QD	Stop treatment
	-3	5 QD	Stop treatment	
	-4	Stop treatment		

MPN-RC

A Phase II Open-label Study of Combined Ruxolitinib and Enasidenib Sinai in Patients with Accelerated/Blast-phase Myeloproliferative Neoplasm or Chronic-

phase Myelofibrosis with an IDH2 Mutation

(Myeloproliferative Neoplasms Research Consortium [MPN-RC] 119)

 Table 3a. Enasidenib Dose Adjustment for thrombocytopenia

MF chronic phase Cycle 1	MF chronic phase Cycle 2 and above	MF chronic phase Cycle 2 and above	MF chronic phase Cycle 2 and above	MF accelerated phase and blast phase
Platelet >75X10 ⁹ /L	Platelet > 50X10 ⁹ /L	Platelet 35-50X10 ⁹ /L	Platelet<35X10 ⁹ /L	Any platelet count
50mg	100mg	50mg	Hold	100mg

Table 3b. Enasidenib Dose Adjustment for non-hematological AE

Dose Level	Enasidenib
-1	50 mg QD
0	100 mg QD

MPN-RC

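### Section 27 stops treatment for toxicity that has not returned to baseline, while Sections 10.1 and 10.1.1 keep the same patient on a reduced dose; the recovery standards need to be reconciled

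*Combined protocol and SAP*

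**What the plan says.** Section 27 opens with "Treatment with study drugs is to be discontinued when any of the following occurs". One item on its list is "Toxicity requiring dose modification/treatment suspension, without recovery to baseline, in a patient with less than a CRi". It gives no grade, no waiting period and no cohort. The same list asks that "any effort should be made to provide therapy to the patient in a safe way for at least 3-6 cycles".

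Section 10.1 deals with the same events differently. After drug-related Grade 3 non-hematologic toxicity the dose is interrupted, and a further course one level lower is allowed, provided "the patient must have recovered to Grade ≤ 1 before initiation of the next course". For chronic Grade 2 non-hematologic toxicity the physician may lower the dose, and no recovery condition is attached.

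Section 10.1.1 allows enasidenib to be reduced without interruption for Grade 2 QTcF prolongation. After Grade 3 it may be resumed at a reduced dose once QTc is within 30 ms of baseline or below 450 ms within 14 days.

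For chronic-phase patients, dosing also follows platelet counts, through "Table 2b. Ruxolitinib Dose Adjustment for patients with chronic phase MF for thrombocytopenia or nonhematological AEs" and "Table 3a. Enasidenib Dose Adjustment for thrombocytopenia". Section 10.2 adds restart levels for ruxolitinib and enasidenib after very low counts.

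Section 3 says that after cycle 6 "patients will continue treatment if response was deemed a CR/CRi/PR or CBR for MPN-AP and MPN-BP patients". For chronic phase it lists CR, PR and clinical improvement as responses.

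**The concern.** Section 27 and Section 10 both decide whether a patient with incompletely resolved toxicity stays on treatment, and they use different recovery standards. No other section says which governs. Section 11.3 sends sites to Section 11 for removal criteria, and Section 11 does not contain the Section 27 trigger. Eleven centers are named in Section 4, so different sites could handle the same patient in opposite ways.

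This reaches the primary endpoint. Under Section 20.1 every eligible, treated patient who does not meet the response definition is a non-response. A patient taken off before responding stays in the denominator as a failure, so the response rate and the discontinuation rate could depend partly on which section a site reads.

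**Working it through.** **1. The provisions side by side.**

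| Situation | Section 10 | Section 27 (patient below CRi) |
|---|---|---|
| Grade 3 non-hematologic, recovered to Grade 1, none at entry | May resume one level lower (10.1) | Discontinue: not at baseline |
| Chronic Grade 2 non-hematologic, dose lowered | May continue; no recovery needed (10.1) | Discontinue while above baseline |
| Grade 2 QTcF, dose lowered | May continue without interruption (10.1.1) | Discontinue if not back to baseline |
| Grade 3 QTcF, back to within 30 ms of baseline | May resume at a reduced dose (10.1.1) | Discontinue: not at baseline |
| Defined hematologic toxicity (Grade 4 neutropenia with unresolved fever, or Grade 4 thrombocytopenia with significant bleeding) | Recovery to baseline grade required (10.1) | Same standard; no conflict |

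An illustration of the fourth row: a patient who enters at 445 ms may resume at up to 445 + 30 = 475 ms. That is above the 450 ms entry ceiling in Section 8.2 and is not baseline. The first row does not arise for a patient who already had the finding at Grade 1 on entry.

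**2. Which cohort is affected.** In accelerated and blast phase, Section 10.2 and Table 3a hold the dose constant whatever the counts, so the conflict runs only through non-hematologic toxicity (10.1 and 10.1.1). In chronic phase the entry minimum is a platelet count of 75 × 10⁹/L (Table 1 footnote). Below that level, Table 3a gives 50 mg enasidenib at 35–50, Table 2b doses ruxolitinib in the 20–50 band, and Section 10.2 permits ruxolitinib rechallenge above 20 and enasidenib above 50. Table 2b's 50–100 band is not a clear example, because a patient entering at 75–100 is in it at baseline.

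**3. Timing.** For relapsed or refractory AML, Section 6.3 reports a median of 1.9 months to first response and "the median time to best response was 3.7 months". At 30.4 days a month these are 1.9 × 30.4 = 58 days (about two 28-day cycles) and 3.7 × 30.4 = 112 days (four cycles). Appendix B also requires benefit to last at least 12 weeks. Removal in the early cycles can therefore precede a response or cut short one that has not yet qualified. These medians are for enasidenib in AML, not for this combination or population.

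**4. The design exposed.** Inputs from Section 20.1: null rate 5%, target 25%, stop if 0 of 13 respond, promising if at least 3 of 20 respond.

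- P(early stop) = (1 − p)^13: 0.513 at p = 0.05 and 0.024 at p = 0.25. Table 6 states 0.51 and 0.02.
- P(declared promising) = sum over x ≥ 1 of P(X₁ = x | 13, p) × P(X₂ ≥ 3 − x | 7, p): 0.074 at 0.05 and 0.903 at 0.25. Table 6 states 0.07 and 0.90.

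Table 6 reproduces. The decisions rest on single patients: 0 versus 1 at stage 1, and 2 versus 3 at the end.

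**5. What-if only.** Suppose a share f of would-be responders were removed before a qualifying response, so that the effective rate is 0.25 × (1 − f). The documents give no value for f; the range is an assumption.

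| f | Rate | P(early stop) | P(declared promising) |
|---|---|---|---|
| 0 | 0.250 | 0.024 | 0.903 |
| 10% | 0.225 | 0.036 | 0.854 |
| 20% | 0.200 | 0.055 | 0.786 |
| 40% | 0.150 | 0.121 | 0.586 |

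**6. The CRi threshold.** CRi is part of the primary endpoint but has no definition in Appendix A or B. It is not among the chronic-phase categories in Sections 3 and 20.2 (CR, PR, CI). Whether a PR is below a CRi for this purpose is not stated, although the wording suggests it.

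**The case against.** Several points on the other side stand.

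- A reader might infer that Section 27 cancels the platelet rows of Tables 2b and 3a, so that the two cannot both be followed. The documents do not go that far. Section 10.1 says cytopenias per se are not adverse events and defines hematologic toxicity narrowly, so the tables can be read as platelet-based dosing outside the trigger. However, Section 10.1 also speaks of chronic Grade 3 hematologic toxicity, and Section 10.2 is headed as covering hematological adverse events. What remains is ambiguity, in the descriptive cohort only.
- A reader might infer that Section 27 contradicts Section 3 for patients in PR or CBR. Section 3 is a response-based rule applied after cycle 6, and Sections 4 and 10 already let responders be stopped for toxicity. A patient whose PR has already qualified also remains a responder, because the endpoint is best response.
- A reader might take the lower probabilities in the what-if table as the trial's real power. They are not. Only would-be responders whom Section 27 removes and Section 10 would keep matter, and nothing in the documents says how many there are.
- Section 27 could be read as applying only when toxicity persists after the dose change. That does not resolve the conflict, because Grade 1 is still not baseline for a patient who entered without the finding.
- Section 27's request for 3–6 cycles and the monthly teleconferences in Section 26.13 may soften practice. Neither says which standard governs.

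**Conclusion.** The conflict is real for non-hematologic toxicity, including QTcF prolongation, and it touches the primary cohort: the same patient may be continued under Section 10 and must be discontinued under Section 27. It can change who is counted as a responder in a design where one patient can change either decision. Its size cannot be computed from the documents. No figure in Table 6 is wrong.

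Two lesser points go with it. For chronic phase, it is unclear whether reductions or restarts under Tables 2b and 3a and Section 10.2 fall under the Section 27 trigger. The CRi threshold is undefined in the appendices and does not match the chronic-phase response categories. The conclusion assumes that baseline in Section 27 means the patient's state at study entry, which is how Section 10.1 uses the word for hematologic toxicity.

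**What to change.** Amend the wording in three respects.

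- Reconcile the Section 27 item with Sections 10.1, 10.1.1 and 10.2 and Tables 2b and 3a, so that one recovery standard applies at every site.
- State whether reductions or restarts under the platelet tables fall under the Section 27 trigger.
- Reconcile the CRi threshold with the response categories used in each cohort, and define CRi where the response criteria are given.

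The sponsor's clinical team decides the content; no particular standard is proposed here. The cost is one protocol amendment with IRB approval under Section 25.4, with no added patients or procedures.
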